11.3 Statistical Methods

The primary analysis variable will be the occurrence of pneumonia in both treatment groups (azithromycin vs. placebo), using Fischer's exact test (two-sided, $p=0.10$) and based on 10% in placebo group. Other clinical variables and all pharmacodynamic variables measured *in vivo* and *in vitro* will be analyzed by Fischer's test, by paired t-test, by Mann Whitney test, or by ANOVA using adequate models, as considered best indicated. The list of all clinical and pharmacodynamic variables considered is provided in Section 7.1.1.

Clinical and Pharmacodynamic Variables

Appropriate graphs for key parameters as well as tables for all analyzed variables will be provided. A subpopulation analysis will be attempted for the primary variable and for selected secondary clinical and pharmacodynamic variables, taking into account if patients are considered as being at risk at study entry:

- Treatment with steroid or antibiotherapy
- Lung damage or transplant
- >72 hours of hospitalization prior to intubation

The variables will be analyzed for all patients and for patients without antibiotic therapy or with antibiotics deprived of activity against the colonizing *P. aeruginosa* strain (Subgroup 1) and for patients treated with antibiotics with *P. aeruginosa* activity (Subgroup 2). If no difference between response to study drug treatment (azithromycin vs. placebo) is seen when considering Subgroup 1 and Subgroup 2, all patients will be combined. If feasible, comparisons of response taking into consideration risk factors (e.g. for subgroups with 0, 1, ≥ 2 risk factors) will be attempted. A detailed statistical plan will be prepared by the responsible statistician prior to decoding the study.

Clinical endpoints and outcome variables as well as pharmacodynamic variables may be used as categorical event (yes, no), as raw data (for days, concentration, score for CPIS and APACHE II score, ventilation parameters, CFU, ...), as log transformed data, as differences to baseline, or as % change of baseline. All measured and calculated variables will be presented as listings by time and by treatment and, if indicated, as difference to baseline and as % change of baseline.

Graphs illustrating time effect will be provided.

Safety parameters

Adverse events

Adverse events reported during trial will be listed by treatment. Absolute and relative frequencies of subjects with adverse events (treatment emergent adverse events) will be tabulated by study part, by body system and by dose. Frequencies of subjects with severe and/or related adverse events will be summarized likewise. Local tolerance will be provided by time and by treatment and will be summarized with descriptive statistics for categorized variables by time and treatment.

Laboratory variables

Laboratory findings will be evaluated using a system of predefined changes and clinically significant abnormal values (provided by sponsor), taking into account the investigator's normal ranges. Listings of all variables will be provided by time and by treatment. Descriptive analysis will be presented by time and by treatment.

Physical examination

Listing of all variables will be provided by time and by treatment group. Descriptive analysis for raw data and for changes from baseline will be presented when appropriate.

Blood pressure and heart rate

Listing of all variables will be provided by time and by treatment. Descriptive analysis for raw data and for changes from baseline will be presented by time and by treatment.

ECG

Twelve-lead ECG will be recorded as described in Appendix I, at a speed of 25 mm/sec and calibrated at 10 mm/mV. If a QTc is prolonged (>450 ms or >60 ms vs. baseline), manual checking of QT and calculation of QTc with Bazett's formula will be performed by the investigator for safety purposes. When a patient will have completed treatment, all his ECGs will be transmitted to an experienced cardiologist for manual measurement as per Appendix J. The ECG parameters calculated manually by cardiologist will be used for statistical analysis.

Occurrence of infections

Information on distribution of infections to any bacterial strain will be collected and occurrence compared between study treatment.

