PROOF-OF CONCEPT STUDY TO INVESTIGATE THE IMPACT OF AZITHROMYCIN ADMINISTERED I.V. VS. PLACEBO ON THE PREVENTION OF PNEUMONIA IN VENTILATED PATIENTS COLONIZED WITH *PSEUDOMONAS AERUGINOSA*

Coordinating Investigator

[name], Paris

Centre xx

Principal Investigator

Department

Hospital

Address

City, mail code

Country

List of Centres by Country

Each country centre list will include:

- National Coordinating Investigator
- Each site with:
 - Site number
 - Principal Investigator
 - Subinvestigators
 - Address
- Quintiles Study Monitor(s)

Phase IIa

Multinational and multicentric

Indication

Prevention of pneumonia in ventilated patients colonized with *Pseudomonas aeruginosa*

Objectives

Primary objective

- To assess the clinical efficacy of azithromycin 300 mg i.v., used as a quorum-sensing blocker, compared to placebo for preventing or delaying the occurrence of pneumonia in ventilated patients colonized with *Pseudomonas aeruginosa*

Secondary objectives

- To assess other clinical efficacy variables
- To compare safety profile in target population
- To demonstrate using both *in vivo* and *in vitro* parameters whether azithromycin can be used clinically as a quorum-sensing blocker against *P. aeruginosa*
- To determine whether *P. aeruginosa* can develop resistance to the quorum-sensing blocker effect of azithromycin

- To check whether prolonged treatment with azithromycin may induce resistance to any of 11 antipseudomonal antibiotics (list in Section 6.2.)
- To verify whether emergence of resistance to other bacteriae may be elicited by assessing rate of infections in both study groups (azithromycin vs. placebo)

Design

2-parallel groups, double blind, randomized, placebo controlled, multiple i.v. dose administered once daily

Population

- Intubated patients
- Age 18 to 75 years
- Males and non pregnant females
- Respiratory tract colonized by *Pseudomonas aeruginosa* as documented by tracheal aspirate

Sample size

- Recruit a total of 120 to 240 patients in order to achieve 100 to 200 assessable cases
- Stop recruitment when 10 *P. aeruginosa* pneumonia cases have been documented and confirmed by panel of experts under blinded conditions

Treatments

- 300 mg azithromycin as i.v. solution at 2 mg/mL or saline (placebo), infused daily over 1 hour, until extubation (Day n-1), occurrence of pneumonia (Day x), exitus, or for a maximum of 20 consecutive days (Day 20)

Clinical efficacy (clinical site)

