- Adverse event profile (reported by subject, observed by investigator)
- Local tolerance (only if peripheral infusion site)
- Standard laboratory tests (see Appendix B)
- Blood gases
- Vital signs (blood pressure, heart rate, body temperature)

- 12-lead electrocardiogram (ECG)
- Emergence of non Pseudomonas infections

Statistical procedures

The primary analysis variable will be the occurrence of pneumonia, using Fischer's exact test. Other clinical and pharmacodynamic variables measured *in vivo* and *in vitro* will be analyzed by Fischer's test or chi-square for categorical variables (presence or absence of condition) whereas continuous variables will be compared using the t-test or the Mann-Whitney test, as considered best indicated. Appropriate graphs for key parameters as well as tables for all analyzed variables will be provided.

Descriptive analysis and listings will be produced for all safety variables (laboratory, adverse events, local tolerance).

Study duration and dates

The duration of this study is expected to be approximately 1 year, depending however heavily on number of assessable patients required (100 to 200) to achieve 10 pneumonia cases elicited by *P. aeruginosa*. Subject recruitment proposed is to start in November 2002 with study completion anticipated in Autumn 2003 to include a maximum of 240 cases for achieving 200 assessable patients.

STUDY SCHEDULE

ABBREVIATIONS AND DEFINITIONS

A-aD ₀₂	Alveolar-arterial P _{O2} difference (gradient)
aPTT	Activated partial thromboplastin time
ADR	Adverse drug reaction
AE	Adverse event
AIDS	Acquired immunodeficiency syndrome
ALT	Alanine aminotransferase (SGPT)
ANOVA	Analysis of variance
AP	Alkaline phosphatase
ARDS	Acute respiratory distress syndrome
AST	Aspartate aminotransferase (SGOT)
AUC	Area under the plasma concentration versus time curve over time periods: AUC ₀₋₂₄ , AUC _{0-∞}
BAL	Bronchial alveolar lavage
bpm	Beats per minute
BMI	Body Mass Index = Body weight (kg) / Height (m ²)
BP	Blood pressure
BW	Body weight
CFU	Colony forming unit (10 ^x /mL)
CAP	Community acquired pneumonia
Cl	Total clearance
C _{max}	Maximal plasma concentration
CPIS	Clinical Pulmonary Infection Score (see Appendix I)
CPK	Creatine phosphokinase
CRP	C-reactive protein
CRF	Case Report Form
C _{ss}	Plasma concentration at steady state
CV	Coefficient of variation
C _{xh}	Plasma concentration at end of infusion
DBP	Diastolic Blood Pressure
DR	Dose response
ECG	Electrocardiogram

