5.3 Treatment Assignment

The study medication will be administered only to subjects included in this study following the procedures set out in the study protocol.

Since the screening period is expected to be short, no dedicated **subject numbers** will be allocated in advance but only a simplified code combining centre number (1, 2, 3, ...), letter S (for screening), and the chronological number of entry (1,2,3,...). Thus, in Centre 5, the 11th patient screened would have the subject number **5-S11**, and, in Centre 12, the 2nd patient screened would carry the subject number **12-S2**. This subject number will be used to identify the subject between initiation and completion of screening, with verification of inclusion/exclusion criteria, and on Day -1. Thereafter, starting on Day 1, each subject will be assigned a **randomization number**, both sequentially and in chronological order, which will combine the study site number and a study medication number i.e. #05108 for centre 5 and 8th patient. Each patient will receive the corresponding study medication (placebo or azithromycin), labeled with that same code number. The investigator will record in the CRF the subject screening number and the 5-digit randomization number.

The study medication will be randomly assigned in advance to the randomization numbers taken into consideration the study site (#01101 to 01124 for centre 1) for a maximum of 25 study sites although 20 sites are targeted initially, according to the randomization plan generated by the Biometrics Department of Quintiles for each site and following a balanced basis (equal groups), by blocks of 4. Each centre will have a different allocation schedule. Each centre will initially receive the number of azithromycin vials corresponding to treatment for 25% of committed patients assuming 20 days of treatment (2 boxes of 10 vials per patient) and taking into account the anticipated patient recruitment (8, 12, 16, 20,...) Additional vials will be shipped to each centre based on recruitment and duration of treatment. Supplementary azithromycin vials will be maintained at disposal of centers recruiting beyond original plans or for new centres in case of need. The randomization plans will be stored with the Biometrics Department. Subjects withdrawn from the study will retain their subject number and their randomization number if drug has already been administered. New subjects must always be allotted a new subject number.

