11.5 Sample Size Justification

The sample size proposed is based on the primary clinical variable, ie. occurrence of pneumonia which is estimated at a 10% occurrence of pneumonia in colonized patients under mechanical ventilation. This reflects international clinical experience with patients under mechanical ventilation and respiratory tract colonization with *P. aeruginosa* (Expert Meeting, Paris, November 15, 2001). The majority of the recruited centres can provide historical figures between 10 and 15% occurrence when no prevention therapy to *P. aeruginosa* is applied. This percentage however may fluctuate depending on country, hospital, department, patient subpopulations, season, and specific nosocomial strains at time of study.

The conservative figure of 10% has been elected which should correspond to recruiting 100 patients in the placebo study group for achieving 10 pneumonia cases. Depending on the degree of clinical efficacy

elicited by azithromycin treatment, the total patient figure may thus fluctuate between 200 assessable patients (10 pneumonia in placebo group, 0 pneumonia in active group, i.e. complete protection) and 100 patients (5 pneumonia in placebo group, 5 pneumonia in active group, i.e. no protection). This is based as described above on Fischer's exact test for the primary analysis variable, i.e. occurrence of pneumonia (two-sided, $p=0.10$, 10% in placebo group).

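### Section 11.3 lists a paired t-test where two independent arms are to be compared, conflicts with the synopsis on this, and allows percent change as an analysis scale for CFU and autoinducer data

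*Protocol*

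**What the plan says.** Section 11.3 covers the secondary clinical variables and all in vivo and in vitro pharmacodynamic variables in one sentence. Beside Fisher's test, they are to be analysed "by paired t-test, by Mann Whitney test, or by ANOVA using adequate models, as considered best indicated". No unpaired t-test is named there. Further on, the section lists the forms in which these variables may be used: categorical, raw, or "as log transformed data, as differences to baseline, or as % change of baseline". CFU is among its examples of raw data.

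The synopsis (Statistical procedures) says that "continuous variables will be compared using the t-test or the Mann-Whitney test, as considered best indicated". The word paired does not appear.

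The synopsis describes the design as "2-parallel groups, double blind, randomized, placebo controlled, multiple i.v. dose administered once daily", and Section 5.3 allocates patients "following a balanced basis (equal groups), by blocks of 4". A patient in one arm therefore has no partner in the other. The only matching is in Section 7.3: for the detailed Geneva work, each pneumonia patient is paired with two control patients by site, one from each arm.

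Section 11.3 adds that "A detailed statistical plan will be prepared by the responsible statistician prior to decoding the study". The primary variable has its own test, "using Fischer's exact test (two-sided, $p=0.10$) and based on 10% in placebo group".

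**The concern.** A paired t-test needs two linked values per unit. In this trial that means baseline and follow-up in the same patient, so the test answers whether an arm changed over time. It does not answer whether azithromycin differs from placebo. Section 11.3 does not limit it to within-patient questions, and the synopsis puts an ordinary t-test in its place. An analysis plan written from 11.3 would start from wording that does not fit the design.

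Percent change raises a second question. If counts or autoinducer concentrations spread over orders of magnitude, a few very large ratios dominate the mean and variance of percent change, and a t-test or ANOVA on that scale becomes insensitive.

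Both bear on the secondary objective of showing, in vivo and in vitro, that azithromycin acts as a quorum-sensing blocker. A change common to both arms could be read as a drug effect, or a real difference could be missed.

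**Working it through.** **1. Arm size, from the plan's own figures.** Section 11.5 states: "The conservative figure of 10% has been elected which should correspond to recruiting 100 patients in the placebo study group for achieving 10 pneumonia cases". With 10 cases against 0, 10/0.10 = 100 per arm, 200 in total. With 5 against 5, 5/0.10 = 50 per arm, 100 in total. The stated range of 100 to 200 assessable patients reproduces, so 50 and 100 per arm are used below. The protocol gives no power, SD, effect or baseline correlation for CFU or autoinducers.

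**2. What a paired test does when the drug does nothing.** Assumed: n = 50 per arm and the same fall in both arms. The two-sided level of 0.10 is borrowed from the primary test, since none is stated for secondary variables. The within-patient difference has SD = s × √(2(1 − ρ)), and the expected t is fall/(SD/√n). The critical value on 49 df is 1.68.

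- s = 1.0 log10, ρ = 0.5, fall 0.5: SD of difference 1.0; expected t = 0.5/(1.0/√50) = 3.54; rejection about Φ(3.54 − 1.68) = 97%. Simulation: about 97% in each arm.
- s = 1.5, ρ = 0.5, fall 0.4: SD of difference 1.5; expected t = 0.4/(1.5/√50) = 1.89; rejection about Φ(0.21) = 58%. Simulation: 59% in the azithromycin arm.

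In the first setting, log10 ANCOVA between arms rejected in 9.4% of null runs and Mann-Whitney in 10.4%, close to the nominal 10%. The paired result says nothing about the drug.

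**3. Why the scale matters.** Let D be the within-patient log10 change. Percent change is 100 × (10^D − 1). If D is normal with SD d, the ratio 10^D has coefficient of variation √(exp((2.303d)²) − 1). With ρ = 0.5, d equals s. At s = 0.3 this gives √(1.61 − 1) = 0.78; at s = 1.0 it gives √(200.7 − 1) = 14. Percent change rises strictly with D, so Mann-Whitney on percent change and on D use the same ranks and give the same p-value.

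**4. Power.** Simulated log10-normal baseline and follow-up: 1,500 runs per setting, 50 and 100 per arm, ρ = 0.3, 0.5 and 0.7, a common fall of 0.5 log10, two-sided 0.10. The arm effect was set at (1.645 + 0.842) × s × √(1 − ρ²) × √(2/n), so that log10 ANCOVA has about 80% power. For example, n = 50, s = 1.0, ρ = 0.5 gives 2.487 × 0.866 × 0.2 = 0.43 log10. Ranges are over ρ and arm size.

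| Assumed log10 SD | ANCOVA on log10 | t-test on % change | Mann-Whitney on % change |
|---|---|---|---|
| 0.3 | 79-83% | 51-71% | 61-75% |
| 0.5 | 78-81% | 40-61% | 62-72% |
| 1.0 | 78-80% | 18-39% | 60-72% |
| 1.5 | 78-81% | 10-25% | 60-72% |

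A t-test on the log10 change from baseline gave 62-77% across all settings.

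**5. Which samples are pre-dose.** CFU comes from Aspirate 1 (Section 7.1.2), taken on Day -1 and before infusion on Day 1 (Sections 7.2.2, 7.2.3), so either can serve as baseline. Autoinducer content comes from Aspirate 2 (Section 7.1.3), taken on Day 1 about 6 hours after infusion start. Only Day -1 is pre-dose for it.

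**The case against.** The strongest reply is that 11.3 is a menu. Methods are chosen as best indicated, the scales are ones that may be used, and the choice is deferred to a plan written before decoding. Section 7.3 likewise leaves the final Geneva parameters to a separate document before unblinding. Most of the remedy is already listed: log transformation, differences to baseline, Mann-Whitney and ANOVA. With two arms, one-way ANOVA is the unpaired t-test, and adequate models could include a baseline covariate. Paired tests also have legitimate uses, such as MIC on Day -1 against the last day or the site-matched controls.

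Much of this stands, and it rules out three stronger readings.

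- A reader might infer that the protocol commits CFU or autoinducer data to percent change or to a paired test. It does not; nothing assigns either option to any variable.
- A reader might infer that percent change throws away most of the power. That holds only for a t-test or ANOVA at a wide assumed spread. It fails at SD 0.3 and for Mann-Whitney, and the protocol gives no SD.
- A reader might infer that the 97% or 59% is a false-positive rate of the planned comparison. It is the rate for one arm's before-after test under an assumed common fall, and 11.3 does not say that such a test would be read as evidence of drug effect.

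What the reply does not remove is that 11.3 names the paired version of the t-test without restricting its use, while the synopsis names the plain one. Deferring detail to a later plan does not reconcile two statements already made.

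**Conclusion.** The point holds in limited form. The paired t-test in 11.3 does not fit a comparison of two independent arms and disagrees with the synopsis. This follows from the text and needs no assumption. Percent change is a poor scale for a parametric between-arm test when values are widely spread. The size of that loss rests on assumed SDs of 0.3 to 1.5 log10, correlations of 0.3 to 0.7 and log-normal data, none of which comes from the protocol. Against the log10 change score, which 11.3 already permits, ANCOVA gains only about 3 to 18 points (about 80% against 62-77%), so preferring it is a matter of efficiency rather than correction of an error.

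Only secondary and pharmacodynamic variables of an exploratory Phase IIa study are touched. Severity is minor to moderate.

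**What to change.** In Section 11.3:

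- Replace the paired t-test with an unpaired method for comparisons between arms, in line with the synopsis. Restrict paired tests to within-patient change or the site-matched subset of Section 7.3.
- Compare CFU and autoinducer content between arms by ANCOVA on the log10 value, with arm and the patient's pre-dose log10 baseline, reported as a ratio of geometric means with its confidence interval. Name the baseline: Day -1 or pre-dose Day 1 for CFU; Day -1 only for autoinducer content of Aspirate 2.
- State a substitution value for zero counts and undetectable autoinducer, fixed before decoding, because their log10 is undefined. Keep Mann-Whitney on the change from baseline as the sensitivity analysis.
- Keep percent change for description only.

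The respiration-device measures are taken only at the end of treatment and have no baseline; they would be compared on the log10 scale without adjustment.

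The cost is a few lines of wording and the rule for values below detection. No new sample is needed, as the baseline aspirates are already scheduled.

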4. SELECTION OF SUBJECTS

4.1 Number of Subjects

Recruitment will be stopped after 10 cases of pneumonia to *P. aeruginosa* have been documented in this multicentre study and confirmed by a panel of experts maintained blinded. Based on a 10% occurrence of pneumonia in patients colonized by *P.aeruginosa* in the placebo group, the total number will range between 100 and 200 assessable patients, or between 120 and 240 if applying a 20% dropout rate. The total number of patients recruited will actually depend on the precise % of patients developing pneumonia in the placebo group in each centre and on the degree of clinical efficacy seen in the azithromycin treated group (for more details, see Section 11.5 *Justification for Study Size*).

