4.3 Exclusion Criteria

Subjects presenting with any of the following will not be included in the study:

- Poor prognosis as judged by Apache II score >25
- Pregnant females
- Grossly under- or overweight (BMI <18 or >29)
- Ongoing therapy with a macrolide (clarithromycin, erythromycin, azithromycin, telithromycin)
- Known allergy to any macrolides
- Proven *P. aeruginosa* pneumonia (with documented CFU>10⁴ in BAL or PBS)
- Ongoing antipseudomonal therapy with a susceptible colonizing strain as proven by antibiogramme*

* A list of recommended antibiotics deprived of antipseudomonal activity is provided in Section 6.2 to facilitate the choice of the investigators and to homogenize antibiotic treatment according to type of infections. For patients on antibiotherapy with activity against pseudomonas prior to study entry, they will be maintained in the screening phase for 48 hrs, pending results of antibiogramme on the colonized strain. If found to be susceptible to the antibiotic used, the patient will be excluded from the study; if found to be resistant, the patient will be included in the study (also see Section 6.2)

- Anticipated short duration of mechanical ventilation (≤ 3 days)
- Known drug interaction which could interfere enough with absorption, metabolism, or excretion and thus could decrease efficacy or raise safety concern despite plasma drug monitoring of concomitant therapy (for examples see Section 6.2)
- Severe hepatic insufficiency (type C i.e. score >10 on Child Pugh scale, Appendix A) [Pugh et al 1973]
- Sick sinus syndrome or known long QT syndrome or $QTc >500$ msec
- Recent donation of blood or participation in another clinical trial within 3 months (Europe) or 1 month (USA)
- Any situation exposing the patient to higher risk or possibly confounding results of the study

Any local or country specific regulations must be respected. Any waiver of the inclusion and exclusion criteria listed above must be approved by the investigator and by the monitor on a case-by-case basis prior to enrolling the subject. This must be documented by both the monitor and the investigator.

No subject will be allowed to enroll in this study more than once if study drug was administered. However a patient may be screened on a 2nd occasion under another screening number if he did not meet all inclusion and exclusion criteria in the first instance.

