* Except if isolated *P. aeruginosa* strain resistant or if medically indicated

Patients on antibiotherapy with activity against pseudomonas prior to study entry will be maintained in the screening phase for 48 hrs, pending results of the antibiogram on the colonized strain. If found to be susceptible to the antibiotic used, the patient will be excluded from the study; if resistant, the patient will be included in the study. Patients already included in the study but requiring an antibiotic with activity against the colonizing *P.aeruginosa* strain will be maintained in the study. Statistical analysis will be performed in these patients as a subgroup and combined with remaining patients only if the pattern of response between treatments is found to be similar to patients treated with no antibiotics or with antibiotics deprived of antipseudomonal activity.

When suspicion of *P.aeruginosa* pneumonia is raised by the clinical situation, a diagnostic procedure must be performed (BAL, PBS) before an antibiotic with antipseudomonal activity can be given empirically. In the case *P.aeruginosa* pneumonia has been diagnosed (Day x) by quantitative culture, dedicated antibiotherapy to treat *P.aeruginosa* infection is recommended and the patient should be taken out of the study at that stage.

Except for other macrolides no treatment is forbidden during the study as reflected in the inclusion/exclusion criteria. Few clinically significant drug interactions are expected to impact on azithromycin clearance, metabolism or distribution and thus concomitant therapy should not influence the clinical outcome of this study. However it is prudent to monitor plasma concentration of concomitant drug which could be increase, thus leading to toxicity, when administering:

- Drugs such as theophyllin, digoxin, ergotamine, dihydroergotamine, or triazolam
- Compounds metabolized by cytochrome P450 system such as carbamazepine, cyclosporine, hexobarbital or phenytoine
- Drugs known to increase QTc wave such as selected H1-antihistaminics
- During therapy with anticoagulants such as warfarin should be monitored regularly by prothrombin time as performed in this study

Dosages of concomitant drugs should be adapted for the best interest of the patient if required for efficacy and/or safety reasons.

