7.2.4. Day x (Day of pneumonia)

The day when a diagnosis of established pneumonia or possible pneumonia is made, will be called Day x. Treatment against *P. aeruginosa* pneumonia will be initiated as soon as the diagnosis is confirmed or if this pathogen is considered as a highly likely cause of pneumonia. The Day x procedures will be implemented as completely as possible on that day (similar to Day n-1) and the remaining items will be performed the next day (Day n). The patient will not receive the test drug on the following morning and the patient will be discharged from the study on Day n with safety and physical examination.

In case of suspicion of pneumonia the necessary explorations will be performed in order to lead to a confirmed diagnosis based on the criteria for *P.aeruginosa* summarized in the table presented below:

Investigation	Documented Pneumonia Day x
BAL	$\geq 10^4$ CFU/mL
Or tracheobronchial aspirate	$\geq 10^5$ CFU/mL
Or protected brush specimen (PBS)	$\geq 10^3$ CFU/mL
CPIS* (see detailed score in App. I)	≥ 6

The diagnosis of pneumonia will be confirmed at later stage under double blind conditions by a panel of independent clinical experts prior to stopping the study to ensure that 10 documented cases of *P. aeruginosa* pneumonia have been included in the study for assessment. The data provided will be patient characteristics, symptoms, all CPIS parameters generated, CPIS overall scores, all X-rays collected and results of BAL (or tracheobronchial aspirate or protected brush). Efforts will be made to achieve a total of 10 pneumonia cases in patients who do not receive concomitant therapy with an antibiotic with activity against the isolated *P. aeruginosa* strain, providing however the overall constraint for a maximum of 240 patients entered will not be trespassed.

Post treatment activities will include:

- Tracheal aspirate 2 (for freezing and transfer to Geneva laboratory for investigation), collected early afternoon (usually 6 hours [if Day x] or 30 hours [if Day n and if applicable] after last test drug administration) if patient still intubated and even if antipseudomonal antibiotherapy has been meanwhile initiated
- ECG, 1 to 4 hours late morning Day x
- Blood pressure, heart rate, respiration rate (early afternoon Day x or Day n)
- Lung X-ray whenever possible that day

- Body temperature (tympanic or rectal) ~17:00
- Local tolerance (up to 24 hours)
- Systemic tolerance (up to 24 hours)

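### Sections 6.2 and 11.3 make pooling for the primary comparison depend on antibiotics started after randomisation, contradicting the all-patient analysis in 11.3, and 7.2.4 counts the ten cases differently from the recruitment stop

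*Protocol*

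**What the plan says.** Entry: section 4.3 excludes patients with "Ongoing antipseudomonal therapy with a susceptible colonizing strain as proven by antibiogramme". Section 6.2 repeats this and adds that a patient already in the study who comes to need an active antibiotic stays in.

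Pooling: section 6.2 analyses those patients as a subgroup, to be "combined with remaining patients only if the pattern of response between treatments is found to be similar" to that of the other patients. Section 11.3 calls them Subgroup 2 and says that if no difference in response to study drug "is seen when considering Subgroup 1 and Subgroup 2, all patients will be combined". Neither section gives a test, a threshold or a time window. The sentence in 11.3 that introduces the subgroups also says the variables are analysed in all patients.

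Primary test: occurrence of pneumonia, azithromycin against placebo, "using Fischer's exact test (two-sided, $p=0.10$) and based on 10% in placebo group".

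Treatment of the endpoint: section 6.2 allows empirical antipseudomonal therapy on suspicion of pneumonia once a diagnostic sample has been taken. Under 7.2.4, treatment "will be initiated as soon as the diagnosis is confirmed or if this pathogen is considered as a highly likely cause of pneumonia".

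Case count: section 4.1 says "Recruitment will be stopped after 10 cases of pneumonia to" *P. aeruginosa* have been documented and confirmed by the panel, and the synopsis agrees. Section 7.2.4 says "Efforts will be made to achieve a total of 10 pneumonia cases in patients who do not receive concomitant therapy" active against the isolated strain, within a maximum of 240 patients.

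**The concern.** Because active therapy at entry is an exclusion, membership of Subgroup 2 is, waivers apart, a post-randomisation event. Study drug can influence it, and so can suspected pneumonia, which is on the path to the endpoint. Comparing arms within groups formed this way is not a randomised comparison. Section 11.3 has no time window that leaves out therapy begun for the endpoint itself.

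Two sections then let a look at these groups decide whether patients are combined, and nothing says which result is primary if they are not. With about ten events in total, that look cannot tell similar from different.

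The case count matters because it fixes the size of the trial. Ten confirmed cases overall and ten cases off active antibiotics are reached at different times.

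**Working it through.** **Inputs from the protocol.** Two-sided Fisher test at 0.10 (11.3); placebo rate 10%, "The conservative figure of 10% has been elected" (11.5); 1:1 allocation (5.3); stop at 10 cases (synopsis, 4.1); at most 240 patients entered, corresponding to 200 assessable (synopsis, 7.2.4).

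**Assumed, because the protocol gives no figure.** The share of patients in Subgroup 2, the share of cases on an active antibiotic, and the effect in each subgroup.

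**1. The plan's own size.** No effect: 10 / 0.10 = 100 patients in total. Complete protection: 10 / 0.10 = 100 per arm, 200 in total. Both match 11.5.

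**2. What ten events can show.** Suppose five cases fall in each subgroup, split placebo-azithromycin 5-0 in Subgroup 1 and 2-3 in Subgroup 2: complete protection in one, a reversed direction in the other. With seven placebo cases among ten, the probability of the observed table is C(7,5) x C(3,0) / C(10,5) = 21/252 = 0.083. The opposite extreme, two placebo cases in Subgroup 1, has C(7,2) x C(3,3) / 252 = 0.083. The two-sided p is 0.167, so a test at 0.10 would call this no difference.

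**3. The rule simulated in this design.** Patients enter 1:1 until 10 cases or 240 patients, with a 10% placebo rate and 30-50% of patients in Subgroup 2. Heterogeneity is a Fisher test of arm by subgroup among the cases at 0.10. If it is not significant, all patients are pooled; if it is, either subgroup's own Fisher test at 0.10 may count. The protocol names no test, so this is one way of making its rule concrete.
- 80% protection in Subgroup 1, none in Subgroup 2: the difference is detected in about 9-14% of trials, so the subgroups are pooled in about 86-91%.
- No effect anywhere: pooled in about 97% of trials. Rejection is about 9-10% when always pooled and about 10-11% under the rule.

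A different choice, a Wald interaction test at 0.10 with relative risk 0.3 in Subgroup 1, 1.0 in Subgroup 2, 20-50% of patients in Subgroup 2 and 154-200 patients (about 11-16 expected cases), gives 22-30%. The conclusion is the same.

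**4. If the split did carry the result.** With relative risk 0.3 throughout and the ten-case stop, the pooled test has about 53% power. If half the cases but 20% of non-cases fall in Subgroup 2 (assumed), Subgroup 1 keeps about 5 of the 10 cases and its power falls to about 22%.

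**5. The two case counts.** If a share q of cases is on an active antibiotic, ten cases off it need 10 / (1 - q) cases overall. For q = 0.1 this is 11.1; for q = 0.5 it is 20. In assessable patients the range 100-200 becomes 100/(1 - q) to 200/(1 - q): 111-222 at q = 0.1 and 200-400 at q = 0.5. With complete protection, any q above zero exceeds the 200 assessable patients that the cap corresponds to.

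**The case against.** Several stronger readings are tempting, and the text does not support them.

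A reader might infer that every case treated on Day x moves to Subgroup 2, leaving Subgroup 1 almost without events. The wording of 11.3 permits this literally. But 6.2 describes the subgroup as patients who stay in the study, and says a patient with diagnosed *P. aeruginosa* pneumonia should leave it. The aim in 7.2.4 could hardly be met on the literal reading. What stands is that no time window is written and that empirical therapy on suspicion can precede confirmation. Even if only earlier therapy counts, the subgroup is still formed after randomisation.

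A reader might say there is no primary analysis. There is: 11.3 names one test and has the variables analysed in all patients. The defect is that the conditional sentences in 11.3 and 6.2 contradict this.

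A reader might see two firm stopping rules. The stop in the synopsis and 4.1 is firm; 7.2.4 states an effort, capped at 240 patients. They still point to different moments for ending recruitment.

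Nor does the rule seriously inflate type I error, and it would usually end in pooling. Both are fair and limit the practical damage. They also show that the check adds almost nothing while leaving the primary result open.

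Finally, 11.3 promises a detailed statistical plan before decoding. That can supply missing detail, but this conditional rule is already fixed in two protocol sections and the plan would inherit it.

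**Conclusion.** The point holds as a contradiction over the primary comparison together with an uninformative pooling condition. The wording conflict and the post-randomisation nature of Subgroup 2 rest on the text alone. The detection rate of about 9-14% rests on the assumed effects, subgroup share and test; under the alternative check it is still no more than about 30%. The change in null rejection, about one percentage point, is minor. The main harm is that a split formed after randomisation, and possibly related to the outcome, is allowed to decide which population carries the primary result. The resulting bias cannot be sized from the protocol.

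The case-count conflict is real but softer. Its size, 11-20 cases instead of 10, depends on an assumed 10-50% of cases being on an active antibiotic and is limited by the cap.

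**What to change.** - In 11.3 and 6.2, state that the primary Fisher comparison is made once, in all patients of the protocol's efficacy population (11.2), regardless of antibiotics given on study. Delete the sentences that make combining conditional. This leaves the 11.2 population as it is.
- Keep the Subgroup 1 and 2 split as descriptive, and count for it only active antibiotics started before suspicion of pneumonia.
- Reconcile 7.2.4 with the synopsis and 4.1 so that one case-count rule governs the end of recruitment. The simplest is ten panel-confirmed cases overall; which rule to keep is the sponsor's choice.

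The cost is wording in three sections. The pooled estimate may be somewhat diluted by patients who received active antibiotics, and the descriptive split will show this.
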